14.3 Efficacy Data Analyses

14.3.1 Primary Efficacy Analyses

The baseline for the primary endpoints will be the pre-dose at each visit.

Superiority comparison of ARS-1 1 mg vs. placebo and ARS-1 2 mg vs. placebo at each timepoint will be tested at the two-sided 0.05 significance level. If both ARS-1 1 and 2 mg are statistically superior to placebo, comparison between the ARS-1 doses will be conducted.

Time to effect is defined to be the time that it takes to lower one grade, two grades, and three grades.

Duration of effect is defined as the time from when the grade becomes above baseline until the grade returned to baseline.

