| Statistical Analysis | 
All quantitative endpoints will be analyses using linear mixed models with fixed effects for treatment and period and a random effect for subject. For each endpoint, the following comparisons will be made using two-sided tests at the $\alpha=0.05$ level of significance:
 
 1 mg ARS-1 vs Placebo 2 mg ARS-1 vs Placebo 
There will be no adjustments for multiplicity; hence, all analyses will be viewed as exploratory and hypothesis generating, rather than confirmatory.
 |
| Study Duration | 
It is anticipated that each subject will participate in the study for up to 120 days, which comprises a 90-day screening period and 3-4-week study period during which three acute flares of urticaria symptoms will be treated.
 |
| Study Centers | 
Up to Four (4) Centers
 |

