3.3 Efficacy Assessments

The following efficacy assessments will be evaluated based on self-reported and clinical assessments of pruritus at pre-dose, and at 5 (± 2 min), 10 (± 2 min), 15 (± 3 min), 30 (± 5 min), 45 (± 5 min), 60 (± 10 min), 120 (± 10 min) minutes, and every 60 minutes (± 10 min) after dosing until the discharge criteria (the time when symptoms of acute urticaria have been effectively treated based on the investigator's or his/her designee's opinion will be recorded, not necessarily when subjects discharged) is met for acute flare and until urticaria symptoms returns to the baseline for chronic spontaneous urticaria. If the time to return to baseline for chronic spontaneous urticaria is beyond 4 hours, such time may be recorded by the patient and reported in the follow-up call. The actual time of the assessment and of when the symptoms return to the baseline will be recorded. Subjects should also record the date and time of recurrence, if any, of symptoms after they leave the clinic.

- A patient reported pruritus/hive score from 0 (none) to 3 (severe) for itch and hive using Uniform Assessment System (UAS) twice daily as below:

| Itch Severity Score | Amount of Itch | Itch Severity at Each Assessment |
|---------------------|----------------|--|
| 0 | None | None |
| 1 | Mild | Minimal awareness, easily tolerated |
| 2 | Moderate | Definite awareness, bothersome but tolerable |
| 3 | Intense | Difficult to tolerate |

| Hive Severity Score | Number of Hives at Each Assessment |
|---------------------|------------------------------------|
| 0 | None |
| 1 | 1-6 |
| 2 | 7-12 |
| 3 | >12 |

- Patient reported pain associated with the urticaria flare will be recorded based on a self-reported VAS score

- An investigator-rated extent of urticaria; % of body area with urticaria (Grade 1: urticarial lesions covering < 10% body surface area [BSA]; Grade 2: urticarial lesions covering 10-30% BSA; Grade 3: urticarial lesions covering > 30% BSA)
- An investigator-rated erythema score (0 = none, 1 = almost clear [slight redness], 2 = mild erythema [definite redness], 3 = moderate erythema [marked redness], 4 = severe erythema [fiery redness])

[REDACTED]

[REDACTED]

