- Patient reported pruritus/hive score and VAS pain assessments will be done pre-dose, and at 5 (\pm 2 min), 10 (\pm 2 min), 15 (\pm 3 min), 30 (\pm 5 min), 45 (\pm 5 min), 60 (\pm 10 min), 120 (\pm 10 min) minutes and every 60 minutes (\pm 10 min) after dosing until the discharge criteria (the time when symptoms of acute urticaria have been effectively treated based on the Investigator's or his/her designee's opinion will be recorded, not necessarily when subjects discharge) is met for acute flare and until urticaria symptoms return to baseline for chronic spontaneous urticaria. The actual time of the assessment and of when the symptoms return to baseline will be recorded.
- Investigator-rated extent of urticaria and erythema will be done pre-dose, and at 5 (\pm 2 min), 10 (\pm 2 min), 15 (\pm 3 min), 30 (\pm 5 min), 45 (\pm 5 min), 60 (\pm 10 min), 120 (\pm 10 min) minutes, and every 60 minutes (\pm 10 min) after dosing until the discharge criteria (the time when symptoms of acute urticaria have been effectively treated based on the Investigator's or his/her designee's opinion will be recorded, not necessarily when subjects discharge) is met for acute flare and until urticaria symptoms return to baseline for chronic spontaneous urticaria. The actual time of the assessment and of when the symptoms return to baseline will be recorded..

[figure not shown]

g.
i.

[REDACTED]

Discharge assessment will be done by Investigator or his/her designee once symptoms of urticaria have been effectively treated for an acute flare or returned to baseline for chronic spontaneous urticaria. Actual time by hour and minutes will be recorded. If the rescue medicine was required, it will be recorded.

[REDACTED]

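### Superiority tests at 180 minutes and later would compare subsets selected by response to treatment; the direction of the bias is clear for acute flare only

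*Combined protocol and SAP*

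**What the plan says.** - **Tests.** Section 14.3.1 sets a "Superiority comparison of ARS-1 1 mg vs. placebo and ARS-1 2 mg vs. placebo at each timepoint", each at two-sided 0.05, and compares the two doses if both beat placebo. It adds: "The baseline for the primary endpoints will be the pre-dose at each visit".
- **Scoring.** Sections 3.3 and 6.0 and Appendix A fix scores at pre-dose and at 5, 10, 15, 30, 45, 60 and 120 minutes. Scoring is then hourly until the discharge criterion (effectively treated, in the investigator's or designee's opinion) "is met for acute flare and until urticaria symptoms returns to the baseline for chronic spontaneous urticaria". Appendix A repeats this for both the patient-reported and the investigator-rated scores.
- **Stay.** Section 3.6 keeps every subject in clinic for at least 2 hours. The bullets in 3.1 and 10.3 state that minimum for acute flare only.
- **Rescue.** The synopsis and 3.1 ask that rescue be avoided, if possible, for 15 minutes. The acute-flare bullets allow it after 2 hours without relief of pruritus.
- **Model and status.** The synopsis specifies "linear mixed models with fixed effects for treatment and period and a random effect for subject" and says that "all analyses will be viewed as exploratory and hypothesis generating, rather than confirmatory".
- **Duration.** Section 14.3.1 gives it a separate definition: "Duration of effect is defined as the time from when the grade becomes above baseline until the grade returned to baseline". Section 3.3 supports this: "The actual time of the assessment and of when the symptoms return to the baseline will be recorded".

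**The concern.** Whether a period still has a score at 180 minutes depends on how the subject responded to that period's treatment. In acute flare, the responders leave and the non-responders stay. In chronic spontaneous urticaria, those who are back at pre-dose leave and those still improved stay. The two groups are pooled, with no condition term in the model and no stated case mix. From 180 minutes on, the contrast is therefore no longer between randomised treatments.

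Taken literally, 14.3.1 still calls these superiority tests, and they could feed the gate for comparing the doses. A reader judging how long the effect lasts, which is part of a primary objective, could take a selection artefact for a loss or a persistence of effect.

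**Working it through.** **1. What is fixed by the text.** Sections 3.3, 3.6 and 14.3.1 together give complete scheduling through 120 minutes, outcome-dependent scoring afterwards, and tests without an upper limit. There is no stated figure on this point to reproduce: section 14.1 bases the sample size (32 subjects in the synopsis) on practical grounds, and no effect size or SD is visible.

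**2. Why the model does not help.** At 180 minutes the model sees only the scored periods. Whether a period is scored depends on the 120-minute state, which is not in the model. A random subject effect borrows strength across a subject's periods but does not restore the missing ones.

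**3. Simulation inputs, all assumed.**
- Itch score 0-3, pre-dose 2 or 3 with equal chance. Each subject gets both doses and placebo.
- Latent improvement = placebo part (0.2, 0.5 or 1.0) + 0.8 on either dose + random terms with SD 0.5 (subject), 0.6 (period) and 0.4 (assessment). Scores are rounded and clipped to 0-3.
- Acute flare stops at 120 minutes if the score is 0, or is at most 1, or has improved by at least 1 grade (three alternative rules).
- Chronic spontaneous stops under one of three readings: (a) score at or above pre-dose; (b) improved at one of six earlier assessments and now back at pre-dose; (c) recovered, score 0.
- The 180-minute change is fitted with treatment and random subject on scored periods only, and the two dose contrasts are averaged. Period is left out: both sequences in 3.1.1 put placebo second, so a period effect cannot be separated from placebo.

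**4. Results at 180 minutes.** True difference 0.66 to 0.70; positive favours ARS-1.

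| Case mix | (a) at or above pre-dose | (b) improved, then returned |
|---|---|---|
| All acute flare | 0.25-0.58 | same (rule not used) |
| 25-75% acute flare | 0.49-0.66 | 0.54-0.74 |
| All chronic spontaneous | 0.41-0.48 | 0.61-0.76 |

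Under (a), all 39 cells, including the nine all-acute ones, lie below the true value. Under (b), about 10 of the 30 cells that contain chronic spontaneous subjects exceed it by more than 0.01. Under (c), those cells give 0.45 to 0.61. In the 25-75% mix under (a), 9 to 27 of 32 ARS-1 periods and 13 to 26 of 32 placebo periods are still scored.

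**5. Effect present at 120 minutes but gone by 180 (true 0).** All acute flare: -0.36 to -0.10. All chronic spontaneous under (a): -0.32 to -0.19. Under (b), with 0 to 50% acute flare and the at-most-1 rule: -0.05 to +0.09. In trials of 32 all-acute subjects (placebo part 0.5, at-most-1 rule), the 180-minute test is significant against ARS-1 in 10%, versus 2-3% if everyone were scored. If ARS-1 has no effect at any time, the estimate stays within 0.01 of 0.

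**6. Cross-check on another scale.** A second simulation used the itch-plus-hive sum (0-6), took a drop of at least 2 points as effectively treated, and assumed its own means and SDs.
- All acute flare: 32% of ARS-1 and 73% of placebo periods are still scored; estimate 0.65 against a true 1.16 (0.65/1.16 = 56%). With a 2-point rescue effect it is 0.08 (0.08/1.16 = 7%).
- All chronic spontaneous: 91% versus 61% still scored under (a), estimate 0.83 against 1.16; under (b), 1.19 against 1.17.
- All chronic spontaneous under (a), with responder/non-responder outcomes (50% versus 10% responding): 1.34 against 1.17, an overstatement.

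**The case against.** **The analyses are exploratory.** This stands. No confirmatory claim is at risk, and duration of effect does not rely on late score tests.

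**Only the seven fixed times may be meant.** Possible. The visible text does not say so, and the fix would then only record the intent.

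**A rule may be redacted.** Section 14.5 and part of the efficacy row in 14.2 are blacked out and could contain a limit or a missing-data rule. This stands and limits confidence.

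**A reader might infer that late tests mainly understate ARS-1 overall.** The documents do not support that. It follows for acute flare. For chronic spontaneous urticaria it depends on reading (a) or (c), and even (a) can overstate with responder-type outcomes. The word return, and a duration definition that runs until the grade has returned to baseline, both make (b) plausible. Under (b) the estimate ranges from somewhat below to somewhat above the true value.

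**A reader might also infer that the 5 to 120 minute tests are free of outcome-dependent problems.** They escape this stopping rule because of the stay in 3.6. But rescue is discouraged only for 15 minutes, so scores from 30 minutes on may follow rescue, and no rule for such scores is visible.

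**Conclusion.** The concern holds in this form. Followed literally, 14.3.1 runs superiority tests at 180 minutes and later on periods selected by response, and the treatment, period and random-subject model does not remove that selection. If ARS-1 works, the bias in acute flare is toward understating it, and more so when rescue follows at 2 hours. In chronic spontaneous urticaria and in a mix, the direction depends on what return to baseline means and on a case mix and response pattern that the documents do not give.

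The sizes shown rest entirely on assumed inputs. They cover 180 minutes and the itch or itch-plus-hive scores, not pain, extent or erythema. Apart from the one rescue run, they leave rescue out, so they illustrate the problem and do not forecast this trial's data. Harm is minor to moderate, and confidence is medium because of the redactions. The change is worth making since it does not depend on the sign of the bias.

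**What to change.** 1. In 14.3.1 state: *Superiority tests are made at 5, 10, 15, 30, 45, 60 and 120 minutes. Later scores are summarised descriptively by treatment and by acute-flare or chronic spontaneous group, with the number still scored and the number who have received rescue.*
2. Repeat the 2-hour minimum stay of 3.6 in the chronic spontaneous bullets of 3.1 and 10.3.

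The cost is two sentences and a short phrase in two places, with no new data. The downside is that there is no formal test after 120 minutes; duration of effect keeps its own time-based endpoint.

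Adjusting for the 120-minute score by arm and condition is a weaker alternative. In the second simulation it recovered about 1.15 to 1.21 against a true value of about 1.16 when outcomes were roughly normal. With 50% versus 10% responding it failed: 0.16 against 1.16 for all acute flare, and 2.02 against 1.17 for all chronic spontaneous.

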| Sample Size | 32 subjects (urticaria patients) |
| Study Population | Adult volunteers aged 18 to 65 years diagnosed with urticaria who experience an acute flare of symptoms or have chronic spontaneous urticaria at least two (2) times a week while on a chronic treatment regimen. |
| Main Inclusion Criteria | 
For a subject to be eligible for this study, he or she must meet all of the following criteria:
 
 1. Is a male or female subject between the ages of 18 and 65 years, inclusive. 2. Has been clinically diagnosed with acute flares or with chronic spontaneous urticaria with unknown etiology and have urticaria symptom (patient-rated pruritus and hive severity score ≥ 2) at least two (2) times a week while on a chronic treatment (e.g., |

| | |
|--------------------------------|--|

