3.1.1 Randomization/Assignment to Study Drug

subjects with urticaria who experience acute flares while on a chronic treatment regimen or chronic spontaneous urticaria with unknown etiology at least two (2) times a week will be enrolled and randomized to receive the following treatments in each Treatment Period:

- 1 mg/100 μ L dose of ARS-1,
- 2 mg/100 μ L dose of ARS-1,
- placebo

To ensure proper wash-out between the IN doses, each subject will be randomized to one of the following sequences:

- 1 mg ARS-1 IN: placebo: 2 mg ARS-1 IN
- 2 mg ARS-1 IN: placebo: 1 mg ARS-1 IN

The side (right or left) of dosing will be alternated per randomization.

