14.0 STATISTICAL CONSIDERATIONS

14.1 Sample Size Determination

The sample size is based on practical consideration. [REDACTED]

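### The 2 mg versus 1 mg comparison is made only if both doses beat placebo, a condition that controls no error rate and withholds the dose estimate when only one dose works

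*Combined protocol and SAP*

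**What the plan says.** Section 14.3.1 compares each ARS-1 dose with placebo "at each timepoint will be tested at the two-sided 0.05 significance level". It then adds: "If both ARS-1 1 and 2 mg are statistically superior to placebo, comparison between the ARS-1 doses will be conducted". It does not say whether this condition applies per timepoint, per endpoint or to the trial as a whole.

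The Statistical Analysis row of the synopsis lists only the two placebo comparisons. The model there has "fixed effects for treatment and period and a random effect for subject". On error control it says: "There will be no adjustments for multiplicity; hence, all analyses will be viewed as exploratory and hypothesis generating, rather than confirmatory".

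The synopsis gives a sample size of 32. Section 14.1 says "The sample size is based on practical consideration"; the rest of that section is blacked out, as is section 14.5. Section 3.1.1 gives two sequences, 1 mg then placebo then 2 mg, and the reverse: "2 mg ARS-1 IN: placebo: 1 mg ARS-1 IN".

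**The concern.** A rule that tests one hypothesis only after others are rejected is normally there to protect a familywise error rate. This plan claims no such protection, so the condition only decides which estimates are shown.

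Two things follow. First, if 2 mg beats placebo and 1 mg does not, the visible plan provides no comparison of the doses. The reader is left to infer a difference from one significant and one non-significant result, which is not a test of that difference. Section 3.2.2 adds the 1 mg dose on the argument that the relevant receptor effect starts at lower exposure, so how 1 mg compares with 2 mg is a natural question for this trial.

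Second, requiring 1 mg to be significant selects trials in which the 1 mg estimate happened to be high. In those trials 2 mg minus 1 mg is pulled towards zero, which could make the lower dose look closer to the higher one than it is.

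**Working it through.** **No figure to reproduce.** The visible text gives no power, effect size or SD. Effects below are assumed, in units of the within-subject SD.

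**Assumptions.** There are 32 subjects (synopsis) with complete data in three periods, approximately normal estimates, and treatment orders balanced over periods. The last is not what section 3.1.1 provides (see the final step). The 0 to 3 itch and hive scores are ordinal, so normality is an approximation.

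**Precision.** Each pairwise contrast has SE = sqrt(2/n) = sqrt(2/32) = 0.25 SD. Residual df = 96 observations − 32 subjects − 2 period − 2 treatment = 60, so the two-sided 0.05 cut-off is t = 2.00. A dose beats placebo when its observed advantage exceeds about 2.00 × 0.25 = 0.50 SD. The two placebo contrasts share the placebo mean and correlate 0.5.

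**Hand check.** The condition cannot be met more often than the weaker dose beats placebo, which is about P(Z > (0.50 − effect)/0.25):
- effect 0: P(Z > 2.0), about 2.5%
- effect 0.4: P(Z > 0.4), about 34%
- effect 0.5: P(Z > 0) = 50%
- effect 0.8: P(Z > −1.2), about 88%
- effect 1.0: P(Z > −2.0), about 98%

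**Simulation.** Same set-up, both placebo contrasts required to be significant in favour of ARS-1:

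| 1 mg / 2 mg effect | True difference | Condition met | Mean difference when met |
|---|---|---|---|
| 0 / 0.8 | 0.80 | 2.5% | about 0.51 |
| 0.4 / 0.8 | 0.40 | 34% | 0.28 |
| 0.5 / 1.0 | 0.50 | 50% | 0.41 |
| 0.75 / 1.25 | 0.50 | 84% | 0.47 |
| 0.8 / 1.2 | 0.40 | 88% | 0.37 |
| 1.0 / 1.4 | 0.40 | 98% | 0.39 |
| 0.2 / 0.2 | 0 | 4% | 0 |
| 0.4 / 0.4 | 0 | 20% | 0 |

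The simulated frequencies in the unequal-dose rows match the hand check, so the weaker dose's power against placebo drives the condition. At 0.4/0.8, only 2 mg is significant in 54% of trials.

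**Chance of reporting a significant dose difference, with and without the condition.** At 0/0.8 it is 1.4% against 88%. At 0.5/1.0 it is 18% against 50%. With an assumed 20 complete subjects at 0.5/1.0, the condition is met 33% of the time and the figures are 6% against 34%.

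**False dose claims.** With equal doses at n = 32 and a normal cut-off of 1.96, the type I error of the dose comparison, given that it is made, ranged from 0.001 to 0.044 over the effects studied. It is conservative, not inflated.

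**Without the condition.** The dose estimate is unbiased, with a 95% CI half-width of about 2.00 × 0.25 = 0.50 SD.

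**Section 3.1.1 sequences.** Placebo is second in both. With an intercept, two period terms and two treatment terms, the fixed-effects design has rank 4 for 5 columns. Neither placebo contrast is estimable, because placebo coincides with period 2. The 2 mg minus 1 mg contrast is estimable. The percentages above therefore describe a balanced design and are illustrative for this one.

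**The case against.** The stated primary objective is ARS-1 against placebo, and no visible objective concerns the choice between doses. Comparing active doses only after both have beaten placebo is a familiar stepwise convention. The trial is labelled exploratory, nothing forbids a descriptive dose difference, and the blacked-out section 14.5 may contain further analyses. These points stand and limit the seriousness. They do not give the condition a purpose, because the plan disclaims the error control that would justify it.

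A reader might infer that the comparison is withheld precisely when the doses differ, or in most trials. The documents do not support either. The condition follows the weaker dose's result against placebo: it is met 84% to 98% of the time in the scenarios where both doses work well yet differ, and is mostly unmet when the doses are equal but weak. With no SD or effect size in the documents, the plausible range runs from about 2.5% to 98%. Section 3.2.2 expects activity at 1 mg, so a true 1 mg effect of zero is the extreme case.

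A reader might also infer that the comparison is always biased when made. It is not: bias is zero for equal doses and at most about 0.035 SD in the three scenarios with a 1 mg effect of 0.75 or more. Nor would the comparison appear only by chance, since real efficacy at both doses also meets the condition. In section 14.3.1 the words about timepoints belong to the placebo tests, so application timepoint by timepoint is one possible reading, not a stated rule.

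**Conclusion.** The concern holds in a limited form. The condition has no error-control role in this plan. It usually withholds the dose comparison when only one dose works, and it shrinks a true dose difference when the weaker dose has modest power against placebo. In the illustrative scenarios the shrinkage runs from about 0.29 SD (0/0.8, where the condition is rarely met) and 0.12 SD (0.4/0.8) down to about 0.01 SD (1.0/1.4). These sizes rest on assumed standardised effects, complete data and balanced orders.

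The aliasing of placebo with period 2 is a separate and larger defect that needs its own correction. It bears on this point in one way: under the stated sequences and model, the one treatment contrast that can be estimated is made to depend on two that cannot. It does not enlarge the figures above.

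**What to change.** Delete the conditional sentence in section 14.3.1. In its place, state that the 2 mg minus 1 mg difference will be estimated with a 95% CI from the same mixed model, for each endpoint and timepoint, as an exploratory and unadjusted estimate whatever the placebo comparisons show. Add this contrast to the comparison list in the synopsis.

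The cost is a sentence or two of text. No new data, subjects or model are needed, because the contrast comes from the model already planned. The only downside is one more unadjusted exploratory contrast to report. This change does not repair the sequence problem in section 3.1.1, which must be resolved on its own.

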2.0 STUDY OBJECTIVES

2.1 Study Objectives

IM epinephrine injection is indicated in the emergency treatment of allergic reactions (Type I) including anaphylaxis. Both IM and SC dosing of epinephrine is approved by the FDA as efficacious in product labeling in the US. Epinephrine injection is also recommended in medical prescribing guidelines in the US for the management of acute flares with associated angioedema in patients with urticaria. Acute urticaria is typically treated with but often unresponsive to antihistamines and corticosteroids. IM epinephrine is typically efficacious in alleviating urticarial flares. An epinephrine nasal spray (ARS-1) is being developed for patients as a needleless alternative route of epinephrine administration for the treatment of acute urticaria.

| Objective | Endpoints |
|--|--|
| Primary | |
| 
To determine the effect of ARS-1 versus placebo based on a patient reported pruritus/hive score
 
To assess time to effect and duration of effect on acute flares associated with urticaria based on a patient reported pruritus/hive score.
 | 
 • A patient reported pruritus/hive score • Patient reported pain associated with the urticaria flair based on visual analog scale (VAS) • An investigator-rated extent of urticaria; % of body area with urticaria • An investigator-rated erythema score |
| Secondary | |
| To assess the safety and tolerability of ARS-1 in subjects with urticaria after IN administration of epinephrine. | 
 • AEs • Vital signs |
| [REDACTED] | |
| [REDACTED] | |

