4.1 Inclusion Criteria

For a subject to be eligible for this study, he or she must meet **all** of the following criteria:

1. Is a male or female subject between the ages of 18 and 65 years, inclusive.
2. Has been clinically diagnosed with acute flares or with chronic spontaneous urticaria with unknown etiology and have urticaria symptom (patient-rated pruritus and hive severity score ≥ 2) at least two (2) times a week while on a chronic treatment (e.g., antihistamine) at least 2 weeks before dosing and will remain the same throughout the study.
3. Has body weight more than 30 kg and body mass index between 18 and 34 kg/m², inclusive.
4. Has no medical history of hypertension and cardiovascular disease in the last 10 years. Controlled hypertension without beta blocker confirmed by the Investigator is acceptable.
5. At screening, has stable vital signs in the following ranges (after 5 minutes of rest):
 - SBP ≥ 90 and ≤ 140 mmHg
 - DBP ≥ 50 and ≤ 90 mmHg
 - HR ≥ 45 and ≤ 100 bpm

Note: Each BP should be taken after at least 5 minutes rest in a chair with back supported, legs uncrossed, and upper arm bared (slight recline for comfort is permitted). If vital signs are out of range, the Investigator may obtain two additional readings, so that up to 3 consecutive assessments are made within 1 hour.

6. If female, is not pregnant or breastfeeding based on the following:
 - a. agree to the use of highly effective contraceptive methods for at least 2 weeks before baseline until 7 days after the last day of study drug and a negative urine pregnancy test at screening; or
 - b. is of nonchildbearing potential defined as clinically infertile as the result of surgical sterilization (hysterectomy, bilateral tubal ligation, bilateral salpingectomy and/or bilateral oophorectomy); or

- c. is confirmed postmenopausal status (defined as either having amenorrhea for ≥ 12 consecutive months without another cause and documented serum follicle-stimulating hormone (FSH) level > 40 mIU/mL or another documented medical condition (e.g., was born without a uterus)).

NOTE: The following are considered highly effective contraceptive methods: abstinence, hormonal oral contraceptives, injectables, and patches; intrauterine devices; double-barrier methods (synthetic condom, diaphragm, or cervical cap used with spermicidal foam, cream, or gel); Nexplanon contraceptive implant (if implanted within 3 years); and male partner sterilization.

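### Time to effect has no value for a period without a fall in grade, so under the only visible model it would compare responders only; some of the grade falls also cannot be reached from some baselines

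*Combined protocol and SAP*

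**What the plan says.** Section 2.1 makes this a primary objective: "To assess time to effect and duration of effect on acute flares associated with urticaria based on a patient reported pruritus/hive score". Section 14.3.1 then gives the definition, "Time to effect is defined to be the time that it takes to lower one grade, two grades, and three grades", and sets the reference: "The baseline for the primary endpoints will be the pre-dose at each visit". It states that each ARS-1 dose is compared with placebo at each timepoint, and that this "will be tested at the two-sided 0.05 significance level". It names no model for time to effect, and gives no censoring time, no cap and no treatment of rescue.

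The one visible efficacy model is in the Statistical Analysis row of the synopsis: "All quantitative endpoints will be analyses using linear mixed models with fixed effects for treatment and period and a random effect for subject". The same row calls every analysis exploratory, without multiplicity adjustment.

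Section 3.3 defines the scales:
- Patient score: "A patient reported pruritus/hive score from 0 (none) to 3 (severe) for itch and hive".
- Investigator-rated extent starts at "Grade 1: urticarial lesions covering < 10% body surface area [BSA" and ends at Grade 3, with no grade for clear skin.
- Erythema runs from 0 to 4.

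Inclusion criterion 2 (Section 4.1) asks for a "patient-rated pruritus and hive severity score ≥ 2" at least twice a week. That is a frequency criterion for entry; no minimum score at dosing is visible.

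**The concern.** A period in which the score never falls by the required amount has no time to effect under this definition. The plan expects such periods: there is a placebo arm, and Section 3.1 provides for rescue when pruritus has not eased after 2 hours. A mixed model leaves out any period without an outcome value. The loss is informative, because whether a period has a value depends on whether the treatment worked. What remains compares speed among flares that responded, and says almost nothing about how many responded.

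The modified intent-to-treat rule does not help. It asks for efficacy data from two treatments, not for an observed time to effect.

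The thresholds raise a second question. The definition lists falls of one, two and three grades without saying which scale is meant or whether itch and hive are summed. Some falls cannot occur from some starting values. If those periods are counted, they look like failures of treatment.

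**Working it through.** The plan has no figure to reproduce: Section 14.1 puts the sample size on practical grounds, with no visible effect size or power.

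**Step 1. Which falls can occur.** The largest possible fall is the pre-dose grade minus the lowest grade on the scale. The table gives the pre-dose value needed.

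| Scale (Section 3.3) | Range | One grade | Two grades | Three grades |
|---|---|---|---|---|
| Itch or hive | 0-3 | 1 or more | 2 or more | 3 |
| Itch plus hive, if summed | 0-6 | 1 or more | 2 or more | 3 or more |
| Extent | 1-3 | 2 or more | 3 | impossible (3 - 1 = 2) |
| Erythema | 0-4 | 1 or more | 2 or more | 3 or more |

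On extent, no fall is possible from Grade 1, and full clearance is still Grade 1. Baseline is reset at each visit, so a subject may be able to reach a threshold in one period and not in another.

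**Step 2. How many periods have no value.** There are 32 subjects x 3 periods = 96 subject-periods. With response by 120 minutes of p0, p1 and p2 on placebo, 1 mg and 2 mg, the number without a one-grade fall is 32 x [(1 - p0) + (1 - p1) + (1 - p2)]. All rates and times are assumptions.

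- (a) 30/60/80%, equal speed among responders: 32 x (0.70 + 0.40 + 0.20) = 41.6
- (b) 50/65/80%, equal speed: 32 x (0.50 + 0.35 + 0.20) = 33.6
- (c) exponential times, medians 120/75/50 min, giving 51/66/77%: 32 x (0.49 + 0.34 + 0.23) = 33.9
- (d) exponential times, medians 180/100/60 min, giving 40/57/72%: 32 x (0.60 + 0.43 + 0.28) = 41.9

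Placebo contributes the largest share: 22.4 of 41.6 in (a) and 16.0 of 33.6 in (b). On average only about 8, 13, 14 and 10 to 11 of 32 subjects in (a) to (d) have a time on both placebo and 2 mg.

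**Step 3. Effect on the comparison.** I simulated 3,000 trials per scenario, with times read at the planned assessments from 5 to 120 minutes. A random-intercept mixed model with treatment as the fixed effect was fitted twice: to periods with a fall only, and to all periods with no-fall periods set to 120 minutes. Results are for 2 mg versus placebo, two-sided 0.05.

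| Scenario | Responders only: difference, rejection | All periods: difference, rejection |
|---|---|---|
| (a) | -0.4 min, 5.2% | -42.4 min, 94.9% |
| (b) | -0.4 min, 5.3% | -25.5 min, 56.5% |
| (c) | -12.5 min, 15.8% | -23.3 min, 61.2% |
| (d) | -13.4 min, 15.0% | -25.8 min, 73.2% |
| No effect, 50% in each arm | 0.0 min, 4.3% | 0.0 min, 5.4% |

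The simulation standard error is about 0.4 points near 5% (square root of 0.05 x 0.95 / 3,000) and 0.9 points near 57%.

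A check by hand: with equal speed and mean recorded time m among responders, the all-periods difference is (p2 - p0)(m - 120). Scenario (a) gives 0.50(m - 120) = -42.4, so m = 35.2. Scenario (b) gives 0.30(m - 120) = -25.5, so m = 35.0. The two agree, as they should.

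**Limits.** The 120-minute cap is one way of keeping no-fall periods; these are not fits of the time-to-event methods recommended below. The period term is omitted. Both sequences in Section 3.1.1 put placebo second, so with period and treatment both fixed (5 columns, rank 4) neither ARS-1 versus placebo contrast can be estimated.

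**The case against.** Several stronger readings are tempting, and the documents do not support them.

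- **That the plan puts time to effect into the mixed model.** No sentence does so by name. Time to effect stands in the objective column, while the endpoint column lists four scores. The link is an inference from the synopsis rule for all quantitative endpoints. Section 14.5 is redacted and could contain a method. What stands is that the visible primary-efficacy section names none.
- **That the trial would miss an effect on response rate.** It would not miss it altogether. The comparison of scores at each timepoint includes periods that did not respond, so such an effect can appear there. Only the time-to-effect comparison is weakened.
- **That responders-only analysis always shows nothing.** The result of about 0 minutes and 5% follows from assuming equal speed among responders. In (c) and (d) it still finds 12.5 to 13.4 minutes, with low power.
- **That ARS-1 could appear slower.** This is conceivable if ARS-1 adds late responders, but no result here shows it. Significant results in the wrong direction were at most 2.3% in (a) to (d), no more than chance.
- **That a three-grade fall is unreachable in general.** On the 0-3 score named in the objective it is reachable from 3. It is impossible for everyone only on extent, and the plan does not say that extent is meant.

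The exploratory label is fair mitigation. It limits the consequence, but a hypothesis-generating analysis also suffers if it discards most of the information on who responded.

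**Conclusion.** The point holds in limited form. Time to effect, a primary objective, is defined only where a fall occurs, with no named scale and no rule for no-fall or rescued periods. If the visible mixed model is applied, the comparison covers responders only and loses most of any difference in response rate. Under the assumed inputs, 34 to 42 of 96 periods drop out. Rejection is about 5% instead of 57-95% with equal speed, and 15-16% instead of 61-73% when the drug also acts faster. The direction of the loss follows from the definition; its size depends on rates and times that the documents do not give.

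The reachability results are exact arithmetic and need no assumption. This is an improvement that should be made to an exploratory trial, not a fault that invalidates its score comparisons.

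**What to change.** **Section 14.3.1**
- Name the scale: the patient-reported itch and hive scores, as in the objective. State whether they are analysed separately or summed.
- Analyse time to the first fall of at least one grade from pre-dose as time-to-event over a common 0-120 minute window, with a Cox model stratified by subject or a within-subject rank test. Section 3.6 keeps subjects in clinic for at least 2 hours, so the window is available for every period.
- Keep no-fall periods: censored at 120 minutes in the Cox model, ranked last in the rank test. Count a period rescued before a fall as not having reached effect within the window. This is a rule for analysis only and changes nothing about when rescue is given.
- Summarise later assessments descriptively, since follow-up beyond 120 minutes depends on response.
- Restrict the two-grade analysis to periods with a pre-dose score of at least 2, and the three-grade analysis to at least 3.

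**Sections 3.3 and 6.0**
- Add extent Grade 0 = no lesions. A three-grade extent fall is then possible, from Grade 3 only, and need not be dropped.

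**Cost.** Analysis wording and one added category on the eCRF; no new visits or assessments. Recording the percentage of body surface area itself is optional. The restricted two- and three-grade analyses will use fewer periods. If redacted text already holds a time-to-event rule, a cross-reference in Section 14.3.1 settles that part, but not the extent scale. The confounding of placebo with period 2 is a separate problem that this does not repair.
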